### **12.1.5 Missing Efficacy Data Imputations**

The primary method of handling missing efficacy data will be MCMC multiple imputation. This method does not rely on the assumption of data missing at random. Additionally, imputation will be conducted within each treatment group independently, so the pattern of missing observations in 1 treatment group cannot influence missing value estimations in another.

For each efficacy variable (IGA and psoriasis signs), the following steps will be performed to impute missing data:

1. Calculate the number of missing Week 8 values to be estimated by MCMC in each treatment group. Let nmiss be the maximum number of missing Week 8 values among the treatment groups.
2. For each treatment group, create a data set containing subjects with observed values and those needing estimation by MCMC. The missing efficacy data in each data set will be filled in using the MCMC method ‘5 x nmiss’ times to generate ‘5 x nmiss’ data sets. The resulting data set for each treatment group will be combined into 1 complete data set for each imputation. Options will be included in each imputation process to prevent estimating values to be outside the range of expected values for the assessment.
3. Imputed data will be used to determine dichotomized success/failure values.
4. Each complete data set will be analyzed with the appropriate CMH test.
5. CMH statistics will be normalized using the Wilson-Hilferty transformation.
6. The results from these analyses will be combined into a single inference using SAS PROC MIANALYZE.

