**Sample size calculations:**

One hundred forty (140) IDP-122 treated subjects and seventy (70) vehicle treated subjects will have greater than 95% power to detect a statistically significant outcome for a two-sided test with an alpha level of 0.05. This is based on treatment success rates of 33.3% and 9.7% which were observed in V01-118A-201. Success was defined as at least a 2-grade improvement from Baseline in the IGA score and an IGA score equating to "Clear" or "Almost Clear".

This study will be performed in compliance with GCP including the archiving of essential study documents. This protocol follows guidelines outlined by the International Conference on Harmonization (ICH). All data furnished to the investigator and his/her staff, and all data obtained through this study, will be regarded as confidential and proprietary in nature and will not be disclosed to any third party, except for the United States Food and Drug Administration or other regulatory body, without written consent from the sponsor.

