## 12 Statistics

All statistical processing will be performed using SAS® unless otherwise stated. No interim analyses are planned. Except where noted, all statistical tests will be two-sided and will be performed at the 0.05 level of significance.

Descriptive statistics will be used to provide an overview of the efficacy and safety results. For categorical parameters, the number and percentage of subjects in each category will be presented. For continuous parameters, descriptive statistics will include n (number of subjects), mean, standard deviation, median, minimum, and maximum. Appropriate inferential statistics will be used for the primary and secondary efficacy variables.

The primary method of handling missing efficacy data will be the method of Markov Chain Monte Carlo (MCMC) multiple imputation. As a sensitivity analysis, the last observation carried forward method (LOCF) will be used (i.e., the last available on-therapy observation for a subject will be used to estimate subsequent missing data points). No imputations will be made for missing safety data.

A statistical analysis plan (SAP), describing all statistical analyses will be provided as a separate document. The SAP will be finalized prior to unblinding of the study treatments.

Amendment 1, Clinical Study Protocol, 14 October 2015

CONFIDENTIAL

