### **12.1.2 Secondary Efficacy**

Similar to the primary endpoint analyses comparisons will be performed using CMH tests stratified by analysis center. The secondary efficacy endpoints will be:

- Percentage of subjects who show at least a 2 grade improvement and reach Clear to Almost Clear at Week 12 for IDP-122 Lotion verses IDP-122 Vehicle Lotion
- Percentage of subjects who show at least a 2 grade improvement and reach Clear to Almost Clear at Week 6 for IDP-122 Lotion verses IDP-122 Vehicle Lotion
- Percentage of subjects who show at least a 2 grade improvement and reach Clear to Almost Clear at Week 4 for IDP-122 Lotion verses IDP-122 Vehicle Lotion
- Percentage of subjects who show at least a 2 grade improvement and reach Clear to Almost Clear at Week 2 for IDP-122 Lotion verses IDP-122 Vehicle Lotion

Evaluation of the secondary efficacy variables will use a gated sequential procedure starting with the comparisons of the first bulleted item and proceeding onto the next item. The process will terminate if a nonstatistically significant value is observed.

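### The number of imputations is set by missing Week 8 values alone, with no minimum, yet it also governs the Week 12 test that opens the secondary sequence

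*Combined protocol and SAP*

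**What the plan says.** Section 12.1.5 makes multiple imputation the primary method for missing efficacy data and runs it by variable, not by visit: "For each efficacy variable (IGA and psoriasis signs), the following steps will be performed to impute missing data". Step 1 fixes the count: "Let nmiss be the maximum number of missing Week 8 values among the treatment groups". Step 2 then applies it to everything that is missing: "The missing efficacy data in each data set will be filled in using the MCMC method", 5 x nmiss times in each arm. Steps 3 to 6 dichotomize, run the CMH test on each data set, apply the Wilson-Hilferty transformation and pool. The section states no minimum number of imputations, no seed and no limit on Monte Carlo error.

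Section 12.1.2 places IGA success at Week 12 first among the secondary endpoints, followed by Weeks 6, 4 and 2. The order is binding: "Evaluation of the secondary efficacy variables will use a gated sequential procedure starting with the comparisons of the first bulleted item", and "The process will terminate if a nonstatistically significant value is observed". Section 12 sets the level: "all statistical tests will be two-sided and will be performed at the 0.05 level of significance".

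**The concern.** The number of imputations should follow the amount of information missing for the test in hand. Here it follows Week 8, whatever is missing at Week 12. Good Week 8 attendance lowers the count without reducing what has to be imputed four weeks later.

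A pooled p-value from few imputations carries Monte Carlo error. If the Week 12 p-value lies near 0.05, that error can put it on either side of the line, and a non-significant value ends testing of Weeks 6, 4 and 2. A confirmatory conclusion would then depend on the random seed. No planned sensitivity analysis would show this: the LOCF analysis (12.1.6.1) is specified for Week 8 success, and the repeated-measures model (12.1.6.2) uses Weeks 2 to 8.

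**Working it through.** **1. The plan's own figure.** For 140 vs 70 subjects at 33.3% vs 9.7%, two-sided 0.05, exact enumeration of Fisher's test gives a power of 97.97% (normal approximation 98.15%). The stated power of more than 95% in Section 12.8.2 is reproduced. It concerns Week 8.

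**2. Imputations produced by the rule, m = 5 x nmiss.**

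| nmiss at Week 8 (worse arm) | share of 140 | m |
|---|---|---|
| 0 | 0% | 0 (undefined) |
| 1 | 0.7% | 5 |
| 3 | 2.1% | 15 |
| 7 | 5% | 35 |
| 14 | 10% | 70 |

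**3. Simulation of steps 2 to 6.** From the documents: arm sizes 140 and 70, analysis centers of about 10 + 5 (Section 12.1.4), so 210/15 = 14 strata, and level 0.05. Assumed: Week 12 success rates, and 10-20% missing at Week 12 in each arm. Missing outcomes are drawn within arm from the posterior of the success rate. Each data set gets the stratified CMH test and the Wilson-Hilferty z. Pooling uses Q = mean z, T = 1 + (1 + 1/m)B and t = Q/sqrt(T), where B is the between-imputation variance.

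The seed-to-seed SD of Q is sqrt(B/m). At 10% missing B is about 0.112, which gives sqrt(0.112/5) = 0.150, sqrt(0.112/15) = 0.086, sqrt(0.112/35) = 0.057 and sqrt(0.112/70) = 0.040. Simulated seed-to-seed SD of a pooled p-value near 0.05:

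| Missing at Week 12 | m=5 | m=15 | m=35 | m=70 | m=140 |
|---|---|---|---|---|---|
| 10% | 0.020 | 0.011 | 0.007 | 0.005 | 0.0034 |
| 20% | 0.034 | 0.018 | 0.011 | 0.008 | 0.0055 |

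**4. How often two seeds disagree at 0.05 on the same trial data** (1,500 trials per cell). The weak effects are 25% vs 10%, 25% vs 12% and 20% vs 9.7%, in that order.

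| nmiss at Week 8, missing at Week 12 | m | weak effects | 33.3% vs 9.7% | m from Week 12 count | weak effects | 33.3% vs 9.7% |
|---|---|---|---|---|---|---|
| 1, 10% | 5 | 5.9 / 8.1 / 8.5% | 1.7% | 70 | 2.2 / 1.9 / 2.1% | 0.4% |
| 3, 10% | 15 | 4.1 / 5.6 / 4.5% | 0.5% | 70 | 1.7 / 2.5 / 2.0% | 0.4% |
| 7, 10% | 35 | 3.1 / 2.9 / 3.6% | 0.5% | 70 | 1.7 / 2.3 / 1.8% | 0.4% |
| 7, 15% | 35 | 3.4 / 3.9 / 2.9% | 1.3% | 105 | 1.7 / 2.2 / 2.2% | 0.6% |
| 14, 15% | 70 | 2.2 / 2.7 / 2.7% | 0.6% | 105 | 1.8 / 2.3 / 1.5% | 0.3% |
| 14, 20% | 70 | 2.9 / 3.5 / 2.9% | 0.5% | 140 | 1.3 / 2.1 / 1.5% | 0.1% |

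The standard error of a 4% entry is sqrt(0.04 x 0.96/1500) = 0.5 percentage points, so small differences between cells mean little.

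**5. Large m.** The SD falls as 1/sqrt(m). From 0.0034 at m = 140 (10% missing) it becomes 0.0034 x sqrt(140/500) = 0.0018 at 500 and 0.0034 x sqrt(140/1000) = 0.0013 at 1000. A second simulation, with correlated visits and 22% vs 10% at 15% missing, gave disagreement of at most 0.7% at 500 imputations.

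**6. Direction of error.** The main simulation ignores earlier visits as predictors, which overstates B and favours the concern. The excess looks modest: at 15% missing B was 0.171, against 0.15-0.16 in the second simulation.

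**The case against.** The strongest reply is that the larger percentages need an unlucky combination.

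- **Effect size.** The weak Week 12 effects are not in the documents. They make 40-74% of simulated trials significant, and flips are most frequent near 50%. The only rates documented are for Week 8: "This is based on treatment success rates of 33.3% and 9.7% which were observed in V01-118A-201". At those rates disagreement is at most 1.7%. This stands.
- **Joint condition.** The 4-9% range needs nearly complete Week 8 data together with 10% missing at Week 12. With 5-10% missing at Week 8, m is already 35-70. This stands.
- **More missing data at Week 12.** A reader might infer this, since the visit falls four weeks after treatment ends, but no missing rate is given for any visit. Sections 8.3 and 11.1.4 ask early terminators back for the follow-up visit, and Section 11.1.5 has Week 12 assessments done for those who leave after Week 8. The assumption is plausible, not documented. In the other direction, early terminators are asked to complete the Week 8 assessments. If these count as Week 8 values, which the plan does not say, nmiss shrinks.
- **Separate SAP.** Section 12 refers to one, and a seed or a minimum could be set there. The text supplied contains none. But the Week 8-only count is a stated rule, not an omitted detail, so this reply does not remove it.
- **A seed would be enough.** A prespecified seed makes the result repeatable. It does not make a borderline decision less arbitrary, and it does nothing when nmiss is 0.

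**Conclusion.** The rule is faulty as written, and the consequence is small. The number of imputations for the gate-opening Week 12 test depends on the wrong visit and has no floor. It gives 5-15 data sets when nmiss is 1-3 and none when nmiss is 0, even if Week 12 values are missing.

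The chance that the seed decides Week 12 significance is about 4-9% in the worst case (weak effect, 5-15 imputations), about 2-4% with a weak effect and nmiss of 7 or more, and about 0.5-2% at the Phase 2 rates. All three rest on assumed Week 12 effects and on 10-20% missing at Week 12.

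A reader might infer that the secondary conclusions are generally irreproducible or that the primary result is in doubt. The documents support neither. Only a borderline Week 12 result and the secondaries gated behind it are exposed, and at Week 8 the count matches the visit being tested. This is an improvement worth making, not a threat to the trial.

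**What to change.** In step 1 of Section 12.1.5, or in the SAP before unblinding, replace 5 x nmiss by a fixed large number of imputations, for example 500-1000, for all efficacy variables and all visits, and prespecify the seed. This covers nmiss = 0 and brings the seed SD of a p-value near 0.05 to about 0.001-0.002 at 10% missing.

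At the least, define nmiss as the largest number missing at any tested visit (Weeks 2, 4, 6, 8 and 12) in either arm and add a fixed minimum. Redefining nmiss alone closes the mismatch but leaves about 1-2.5% disagreement under the weak effects, so the fixed number is better.

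The cost is one sentence and some computing time. Patients, sites and sample size are unaffected.

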## 6 Study Objectives and Purpose

The objective of the study is to evaluate the safety and efficacy of topical IDP-122 Lotion when applied once daily to adult subjects with moderate to severe plaque psoriasis (defined as an Investigator's Global Assessment [IGA] score of 3 or 4). The intent of the study is specifically to evaluate the safety and efficacy of a once daily application of IDP-122 Lotion in comparison with vehicle.

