### **12.1.6 Sensitivity Efficacy Analyses**

#### **12.1.6.1 Analyses Using Last Observation Carried Forward**

In the first set of sensitivity analyses, missing IGA values will be imputed using LOCF. Treatment success at Week 8 will be analyzed as it was in the primary analyses. Comparisons will be performed on imputed data using CMH tests stratified by analysis center.

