### 12.8.2 Sample Size Determination

The following power calculations were computed using the observed Week 8 dichotomized IGA efficacy data in the ITT population from the Phase 2 study V01-118A-201. SAS PROC POWER with the Fisher's exact test option was used to calculate the power for various sample sizes using a two-sided test with an alpha of 0.05. Table 5 presents the efficacy estimates derived from study V01-118A-201.

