**Table 5. Percent Dichotomized IGA Success for Treatment Groups**

	IDP-122* (IDP-118 Monad (HP 0.01%) Lotion)	IDP-122 (IDP-118) ** Vehicle
Percent Success	33.3%	9.7%

Success was defined as at least a 2-grade improvement from Baseline in the IGA score and an IGA score equating to "Clear" or "Almost Clear".

\*IDP-122 refers to the (IDP-118 Monad (HP 0.01%) Lotion) used in the V01-118A-201 Study

\*\*IDP 118 Vehicle composition used in the V01-118A-201 is equivalent to the vehicle that will be used in this study (IDP 122 Vehicle Lotion).

One hundred forty (140) IDP-122 treated subjects and seventy (70) vehicle treated subjects will have greater than 95% power to detect a statistically significant outcome for a two-sided test with an alpha level of 0.05.

It was noted that the estimates extracted from the above studies are based on the LOCF method of handling missing values while the proposed Phase 3 analysis will account for missing values using multiple imputations. The power stated above sufficiently exceeds 95% which will compensate for the difference in handling of missing data.

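### The primary multiple-imputation analysis pools only a transformed CMH statistic; no pooled treatment difference with a confidence interval is specified

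*Combined protocol and SAP*

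**What the plan says.** Section 6 sets the aim: "The intent of the study is specifically to evaluate the safety and efficacy of a once daily application of IDP-122 Lotion in comparison with vehicle". Section 12.1.1 tests Week 8 treatment success with CMH tests stratified by analysis center, and Section 12.1.2 does the same for success at Weeks 12, 6, 4 and 2, tested in sequence.

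Section 12.1.5 gives the multiple-imputation analysis in six steps. Step 4 runs the CMH test on each completed data set. Step 5 reads: "CMH statistics will be normalized using the Wilson-Hilferty transformation". Step 6 reads: "The results from these analyses will be combined into a single inference using SAS PROC MIANALYZE".

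There are two sensitivity analyses. For LOCF, Section 12.1.6.1 says: "Comparisons will be performed on imputed data using CMH tests stratified by analysis center". Section 12.1.6.2 fits a logistic GEE to Weeks 2 to 8 with treatment, analysis center and visit as factors. It lists no treatment-by-visit term and names no effect measure.

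The Synopsis plans descriptive summaries of the percent with success at each visit, including Week 8, and Section 12 plans counts and percentages for categorical data. Neither says whether these come from observed or imputed data, or how they are combined across imputations. Section 12 also refers to a separate SAP, whose text was not available.

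**The concern.** PROC MIANALYZE returns an estimate and interval for whatever is passed to it. Here that is a normalized chi-square, so the interval describes a test score and not a difference in success rates. If the steps are followed exactly, the primary result is a p-value. Any effect size has to be read off a descriptive table whose handling of missing data is undefined and which carries no standard error and no adjustment for center.

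Two things are at stake. The first is the precision of the primary result, which a reader needs in order to judge benefit over vehicle. The second is the use of the sensitivity analyses. Section 12.8.2 itself notes that the planning rates came from LOCF while this trial will use multiple imputation, so a shift between the two methods is foreseen. The plan specifies no estimate with uncertainty by which to measure that shift.

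**Working it through.** **Inputs.** Success rates, from the Synopsis: "This is based on treatment success rates of 33.3% and 9.7% which were observed in V01-118A-201". Sample size and power, from Section 12.8.2: "One hundred forty (140) IDP-122 treated subjects and seventy (70) vehicle treated subjects will have greater than 95% power". Power method, same section: "SAS PROC POWER with the Fisher's exact test option was used to calculate the power for various sample sizes". Significance level, from Section 12: "all statistical tests will be two-sided and will be performed at the 0.05 level of significance". The documents give no missing-data rate; 5%, 10% and 15% are assumed.

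**1. The plan's own figure.** Exact enumeration of the two-sided Fisher test at 33.3% vs 9.7% with 140 and 70 subjects gives power 0.980. This agrees with the stated figure.

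**2. What would be pooled.** Ignoring centers, the overall rate is p̄ = (140×0.333 + 70×0.097)/210 = 0.254.

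- CMH-type chi-square = (p1 − p2)² / [p̄(1 − p̄)(1/140 + 1/70)] × 209/210 = 0.0557/0.00406 × 0.995 = 13.64.
- Wilson-Hilferty with 1 df: (13.64^(1/3) − 7/9)/√(2/9) = (2.389 − 0.778)/0.471 = 3.42.

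**3. Whether 3.42 identifies an effect.** It does not. With 140 and 70 subjects, all of these give 3.42:

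| IDP-122 | Vehicle | Difference (points) | Odds ratio |
|---|---|---|---|
| 21.3% | 2% | 19.3 | 13.2 |
| 33.3% | 9.7% | 23.6 | 4.65 |
| 57.1% | 30% | 27.1 | 3.1 |
| 12.0% | 33.3% | −21.3 | below 1 |

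The last row shows that the score carries no direction. In an illustrative run with 10% missing, the pooled score had a 95% interval of 1.35 to 5.43, which cannot be converted into a treatment difference.

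**4. What a p-value alone can hide.** Halve the planned difference to 11.8 points (21.5% vs 9.7%). The chi-square is then 4.47 and p is about 0.035, so half the benefit would still be significant.

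**5. The estimate that could be reported.** Complete data, ignoring centers: SE = √(0.333×0.667/140 + 0.097×0.903/70) = 0.0533. The difference is 23.6 points and the half-width is 1.96×5.33 = 10.4, giving a 95% CI of 13.2 to 34.0.

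With missing data, a simple within-arm binomial imputation used five times the larger missing count as the number of imputations m, as Section 12.1.5 prescribes. Results were pooled by Rubin's rules, T = Ū + (1 + 1/m)B, one illustrative run each:

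| Assumed missing | m | Pooled difference (points) | 95% CI |
|---|---|---|---|
| 5% | 35 | 23.9 | 13.2 to 34.6 |
| 10% | 70 | 23.4 | 12.2 to 34.6 |
| 15% | 105 | 23.6 | 12.2 to 35.0 |

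**6. Behavior in small strata.** Complete data were simulated in 14 centers of 10 + 5 subjects with the same rates in every center (40,000 trials). The Mantel-Haenszel risk difference with Sato variance had 94.6% coverage at the planning rates. At an assumed 22% vs 10%, the interval and the CMH test disagreed on significance in about 7.6% of trials. With both arms at 10%, the interval excluded zero in 5.9% of trials, against about 5% rejections by CMH.

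**The case against.** A reader might infer that the trial could say whether IDP-122 beats vehicle but not by how much. The documents do not support that. The endpoint is itself a percentage and Week 8 success by arm is to be tabulated, so a crude difference follows by subtraction. What is missing is a specified pooled estimate with its precision.

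A reader might also infer that the primary and its two sensitivity analyses sit on three scales and cannot be compared. That is too strong. Section 12.1.6.1 analyzes LOCF data with the same center-stratified CMH test as the primary, so only the GEE differs in kind. If imputed and LOCF percentages are tabulated together, a large drop would be visible. The plan also states no rule that robustness is to be judged on significance alone.

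Three further objections have force. The separate SAP may name an effect measure. The gap causes no bias, loss of power or inflation of type I error. Choosing a risk difference over a common odds ratio is partly preference, though it matches an endpoint defined as a percentage.

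Against this, Section 12.1.5 sets out the pooling in full and contains no estimate, and a descriptive percentage with undefined handling of imputation is no substitute for one. Step 6 of the working also shows a real cost of adding an interval: it can disagree with the test, so the plan must say which governs.

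**Conclusion.** The point holds as a gap in specification and reporting. The protocol pools a unitless, unsigned statistic and specifies no pooled treatment difference with a confidence interval for the Week 8 primary, the sequential secondaries or the LOCF analysis. At the planning rates the unreported result is 23.6 points with a 95% CI of about 13 to 34 with complete data, and about 12 to 35 with 10% to 15% missing.

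This rests on the planning rates, on ignoring centers in the interval, on assumed missing rates, and on the protocol text alone. If the separate SAP already specifies such an estimate, a cross-reference closes the point. The primary test and the stated power stand.

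**What to change.** 1. In Section 12.1.5, keep the CMH test as the sole decision rule.
2. From each imputed data set also compute the Mantel-Haenszel risk difference (IDP-122 minus vehicle), stratified by analysis center, with the Sato variance. Pool by Rubin's rules in PROC MIANALYZE and report the difference with its 95% CI for the Week 8 primary and each sequential secondary.
3. In Section 12.1.6.1, report the same stratified difference and CI for LOCF.
4. In Section 12.1.6.2, add a treatment-by-visit term and report the Week 8 contrast as a marginal risk difference with CI. Without that term the model imposes one odds ratio over Weeks 2 to 8, and converting it would not give a freely estimated Week 8 effect.
5. State that the CMH p-value governs and that the interval is for estimation, because the two can disagree near the significance boundary.

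The cost is a few sentences of plan text and a little programming, settled before unblinding. It needs no new data and leaves the sample size, the stated power and the primary test decision unchanged.
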